7.3.1 Primary endpoint analyses

The derivation of the primary endpoint PSS sum intensity score per time point is outlined in [Section 5.6.3](#). The maximum CfB is defined as the maximum of the differences of the PSS sum intensity score measured at each time point after the CCK-4 challenge minus the PSS sum intensity score measured at baseline. Further details on the calculation will be given in the TSAP. The primary endpoint analysis will be performed on the PDS (refer to [Section 7.3](#)).

Primary analyses

The statistical model used for the investigation of the primary endpoint PSS sum intensity score will be a mixed effects model given by

$$y_{imj} = \mu + \pi_m + \tau_j + \gamma b_{im} + \gamma' b'_i + s_i + e_{imj},$$

where

y_{imj} Maximum CfB (absolute change from period baseline) in PSS sum intensity score for the i th subject and the m th period, receiving randomised treatment j ,

μ overall intercept,

π_m m th period effect, $m = 1, 2$,

τ_j j th treatment effect, $j = 1, 2$,

b_{im} baseline value for subject i in period m (period baseline),

γ associated covariate effect of period baseline,

b'_i the subject baseline value (mean of the 2 period baselines) for subject i ,

γ' associated covariate effect of subject baseline,

s_i the random effect of subject i,

e_{imj} the random error associated with subject i who received treatment j in period m.

The last value before administration of the CCK-4 challenge in each period is considered as the corresponding period baseline measurement. The PSS sum intensity score mean value of the two period baseline values is considered as the subject baseline.

The treatment comparison will be the difference between active treatment and placebo. Adjusted means (Least Squares Means) as well as 2-sided 90% CIs will be calculated. Additionally, the difference in adjusted means relative to placebo will be provided. To support this analysis, listings and graphical displays may be generated if appropriate.

As a sensitivity analysis, the same statistical model as stated above will be repeated for the primary endpoint but with all sources of variation considered as fixed effects.

Further details will be presented in the TSAP.

7.3.2 Secondary endpoint analyses

Not applicable.

7.3.4 Safety analyses

Safety will be analysed based on the assessments described in [Section 2.2.2.2](#). All treated subjects (TS, refer to [Section 7.3](#)) will be included in the safety analysis. Safety analyses will be descriptive in nature and based on BI standards. No hypothesis testing is planned.

For all analyses, the treatment actually administered (= treatment at onset) to the subject will be used (any deviations from the randomised treatment will be discussed in the minutes of the Blinded Report Planning Meeting).

Treatments will be compared in a descriptive way. Tabulations of frequencies/proportions will be used to evaluate categorical (qualitative) data, and tabulations of descriptive statistics will be used to analyse continuous (quantitative) data.

Measurements (such as ECG, vital signs, or laboratory parameters) or AEs will be assigned to treatments (see [Section 4.1](#)) based on the actual treatment at the planned time of the measurement or on the recorded time of AE onset (concept of treatment emergent AEs). Therefore, measurements planned or AEs recorded prior to first intake of trial medication will be assigned to the screening period, those between first trial medication intake and end of REP (see [Section 1.2.3](#)) will be assigned to the treatment period. Events occurring after the REP but prior to next intake or end of trial termination date will be assigned to 'follow-up'. In case of two or more treatments, the follow-up will be summarized according to the immediately preceding treatment. These assignments including the corresponding time intervals will be defined in detail in the TSAP. Note that AEs occurring after the last per protocol contact but entered before final database lock will be reported to Pharmacovigilance only and will not be captured in the trial database.

Additionally, further treatment intervals (analysing treatments) may be defined in the TSAP in order to provide summary statistics for time intervals, such as combined treatments, on-treatment totals, or periods without treatment effects (such as screening and follow-up intervals).

Adverse events will be coded using the Medical Dictionary for Regulatory Activities (MedDRA). Frequency, severity, and causal relationship of AEs will be tabulated by treatment, system organ class, and preferred term. SAEs, AESIs (see [Section 5.2.6.1](#)), and other significant AEs (according to ICH E3) will be listed separately.

Previous and concomitant therapies will be presented per treatment group without consideration of time intervals and treatment periods.

Laboratory data will be compared to their reference ranges. Values outside the reference range as well as values defined as possibly clinically significant will be highlighted in the listings. Additionally, differences from baseline will be evaluated.

Vital signs or other safety-relevant data will be assessed with regard to possible on-treatment changes from baseline.

Relevant ECG findings will be reported as AEs.

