total entered	20* *Screening may include more than 60 healthy subjects who will be exposed to CCK-4 to identify subjects with an anxiogenic and panic induced effect in response to CCK-4 as until 20 eligible subjects have been identified
each treatment	20 (all to receive both active treatment and placebo)
Diagnosis	Not applicable
Main criteria for inclusion	Healthy male CCK-4 sensitive subjects, age of 18 to 55 years (inclusive), body mass index (BMI) of 18.5 to 29.9 kg/m ² (inclusive)

Proprietary confidential information © 2019 Boehringer Ingelheim International GmbH or one or more of its affiliated companies

Challenging agent	CCK-4 (CCK B receptor agonist)
dose	50 µg
mode of admin.	iv bolus injection
Test product	BI 1358894 film-coated tablet, strength 25 mg (inhibitor)
dose	100 mg (4 film-coated tablets)
mode of admin.	Oral with 240 mL of water after a standard high-fat meal
Reference product	Matching placebo as film-coated tablet
dose	Not applicable
mode of admin.	Oral with 240 mL of water after a standard high-fat meal
Duration of treatment	2 single doses of CCK-4 and BI 1358894 or placebo (separated by a washout period of at least 17 days between drug administrations), 1 single dose of the provoking agent for the preselection of CCK-4 sensitive healthy subjects
Statistical methods	Descriptive statistics will be calculated for all endpoints. The statistical model to assess the primary pharmacodynamic endpoint PSS sum intensity score will be a mixed effects model including effects for 'treatment', 'period' and 'subject', as well as covariates 'period baseline' and 'subject baseline'. Two sided 90% confidence intervals (CIs) will be calculated based on the residual error from the mixed model.

Proprietary confidential information © 2019 Boehringer Ingelheim International GmbH or one or more of its affiliated companies

FLOW CHART FOR THE SINGLE DOSE CCK-4 CHALLENGE

Period	Visit	Day	Planned time (relative to drug administration [h:min])	Approximate clock time of actual day [h:min]	Event and comment	Safety laboratory	CCK-4 challenge ⁸	12-lead ECG	Continuous ECG monitoring	Vital signs (BP, PR)	Suicidality assessment ⁷	PSS/	Questioning for AEs and concomitant therapy ⁵
SCR	1	-28 to -7			Screening (SCR) ¹	x		x		x	x		
	2	-6 to -2	-0:15	08:00	Screening CCK-4-challenge visit ^{8,13}	x			▲	x		x	x
			0:00	08:15			x		—			x	
			0:05	08:20					—			x	
			0:10	08:25					—			x	
			0:20	08:35					—			x	
			0:30	08:45					▼			x	x ¹⁰

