4.1.4 Drug assignment and administration of doses for each subject

This trial is a 2-way crossover study. All subjects will receive the 2 treatments in randomised order. The treatments to be evaluated are outlined in [Table 4.1.4: 1](#) below.

Table 4.1.4: 1 Dosage and treatment schedule

Treatment	Substance	Formulation	Unit strength	Dosage	Total dose
T (Test)	BI 1358894	Tablet	25 mg	4 tablets (25 mg) q.d for 1 day	100 mg
R (Reference)	Placebo	Tablet	n.a. mg	4 tablets (n.a. mg) q.d for 1 day	n.a. mg

The investigator (or authorised designee) will administer the trial medication as a single oral dose together with about 240 mL of water to subjects who are in a sitting position. For drug administration, the so-called four-eye principle (two-person rule) should be applied. For this, one authorised employee of the trial site should witness the administration of trial medication, and – if applicable – its preparation (e.g. reconstitution), if correct dosage cannot be ensured otherwise.

CCK-4 will be provided in vials containing 50 µg lyophilized CCK-4. Immediately prior to use, 5 mL of sterile normal saline (0.9% NaCl) for injection will be added to the vial containing lyophilized CCK-4 powder and mixed to produce a solution for injection. Before CCK-4 administration, 5 mL (50 µg CCK-4) of the solution is withdrawn from the vial into a syringe. Then the CCK-4 will be administered to the subjects as a bolus injection over 5 seconds (maximum of 8 seconds) via a venous cannula.

In each treatment period, a high-fat, high-calorie meal will be served 30 min before BI drug administration. The subjects must completely consume the meal prior to drug intake. The composition of the standard high-fat, high-calorie meal is detailed in [Table 4.1.4: 2](#); this meal is in compliance with the FDA guidance ‘Food-Effect Bioavailability and Fed Bioequivalence Studies’ [[R03-2269](#)]. For restrictions with regard to diet, see [Section 4.2.2.2](#).

Table 4.1.4: 2

Composition of the high-fat, high-calorie meal

Ingredients	kcal
2 fried eggs (in 15 g butter/margarine) (approximately 100 g)	220
40 g fried bacon ²	151
2 toasted slices of whole-wheat bread	154
15 g margarine for buttering toast slices	112
115 g fried potatoes	130
240 mL whole milk (3.5% fat)	151
Sum¹	918

1 The total caloric content was supplied approximately as following: 156 kcal as protein, 235 kcal as carbohydrate, and 500 to 600 kcal as fat.

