4.2.2 Restrictions

4.2.2.1 Restrictions regarding concomitant treatment

In principle, no concomitant therapy is allowed. All concomitant or rescue therapies will be recorded (including time of intake on study days) on the appropriate pages of the CRF.

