7.7 DETERMINATION OF SAMPLE SIZE

It is planned to enter a total of 20 subjects in the trial, because this sample size is considered sufficient to achieve the aims of this exploratory trial. At least 15 subjects need to be evaluable for the primary objective of this trial.

Based on this sample size, the probability to observe a meaningful reduction in PSS sum intensity score after a single dose of BI 1358894 when compared to placebo is given in [Table 7.7: 1](#) for N=20 subjects and in [Table 7.7: 2](#) for N=15 subjects.

For these calculations, the following assumptions are made. A total of N subjects are evaluable in this cross-over study. The standard deviation of the maximum change from baseline of the treatment contrast of PSS relative to placebo is 20%. The maximum change from baseline for PSS sum intensity score relative to placebo is 0% after the placebo treatment. Six different scenarios are displayed.

Table 7.7: 1 Probability to observe a difference in the primary endpoint $\leq 20\%$, $20\% - 40\%$ and $> 40\%$ relative to placebo for different scenarios and a sample size of N=20 evaluable subjects.

True maximum change from baseline relative to placebo		Probability to observe a relative mean difference (BI 1358894 vs. Placebo)		
BI 1358894	Placebo	$\leq 20\%$	20% - 40%	$> 40\%$
10%	0%	70.9	23.6	5.5
18%	0%	54.4	33.9	11.7
28%	0%	33.0	41.5	25.5
33%	0%	23.8	41.2	35.0
46%	0%	8.2	28.9	62.9
52%	0%	4.5	21.0	74.5

Table 7.7: 2 Probability to observe a difference in the primary endpoint $\leq 20\%$, $20\% - 40\%$ and $> 40\%$ relative to placebo for different scenarios and a sample size of N=15 evaluable subjects.

True maximum change from baseline relative to placebo		Probability to observe a relative mean difference (BI 1358894 vs. Placebo)		
BI 1358894	Placebo	$\leq 20\%$	20% - 40%	$> 40\%$
10%	0%	68.2	23.3	8.6
18%	0%	53.8	30.9	15.4
28%	0%	35.3	36.1	28.6
33%	0%	27.1	35.9	37.0
46%	0%	11.6	27.3	61.2
52%	0%	7.3	21.3	71.4

Proprietary confidential information © 2019 Boehringer Ingelheim International GmbH or one or more of its affiliated companies

The calculations were performed using R version 3.3.2. The R code for the sample size calculations will be documented in a separate file and stored in the Trial Master File (TMF).

8. INFORMED CONSENT, TRIAL RECORDS, DATA PROTECTION, PUBLICATION POLICY, AND ADMINISTRATIVE STRUCTURE

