7.2 CONCOMITANT DISEASES AND MEDICATION

Concomitant diseases will be coded according to the most recent version of MedDRA. Concomitant medication will be coded according to the most recent version of the World Health Organisation – Drug Dictionary.

Only descriptive statistics are planned for this section of the CTR.

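### The planned summary of concomitant therapy ignores treatment period, so in this crossover it cannot compare therapy use on BI 1358894 with placebo

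*Protocol*

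**What the plan says.** The rule is in Protocol Section 7.3.4: "Previous and concomitant therapies will be presented per treatment group without consideration of time intervals and treatment periods". The design is a two-way crossover; Protocol Section 4.1.4 states: "All subjects will receive the 2 treatments in randomised order".

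The same Section 7.3.4 opens with a different general principle: "For all analyses, the treatment actually administered (= treatment at onset) to the subject will be used". Measurements and AEs are attributed to treatments on that basis.

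The SAP leaves the therapy rule in place. Section 7.2 gives the coding dictionaries and then: "Only descriptive statistics are planned for this section of the CTR". Section 4 says the protocol's analyses will be carried out, and the only changes it lists concern the enrolled and entered sets. Table 6.1: 1 defines a phase for each treatment, but for AEs only. Section 6.1 analyses laboratory data and vital signs by treatment period.

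The data for a period-specific table are collected. Protocol Section 4.2.2.1 states: "All concomitant or rescue therapies will be recorded (including time of intake on study days) on the appropriate pages of the CRF".

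**The concern.** A table by group that ignores period suits a parallel-group trial, where each subject belongs to one group. Here each subject is planned to receive both treatments. Once period is set aside, nothing in the table links a therapy to the treatment the subject was on when he took it.

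The comparison has some value. Protocol Section 4.2.1 lets the investigator authorise symptomatic therapy for AEs, and Section 5.2.6.1.4 singles out headache for daily follow-up. Section 7.3 makes use of restricted medication a possible reason to exclude PSS data. Whether therapy was needed more often on one treatment is therefore a tolerability observation and a background check on the PSS comparison. A reader of the report would look for it in this table and could take equal columns as evidence of no difference.

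**Working it through.** The plan gives no figure for therapy use, so there is nothing to reproduce. The check is a count of who lands in which column.

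**Inputs from the documents.** 20 subjects, all planned to receive both treatments (Protocol Synopsis and Section 4.1.4). A minimum of 15 evaluable: "At least 15 subjects need to be evaluable for the primary objective of this trial" (Protocol Section 7.7). Some subjects may therefore have only one period. The numbers of therapy users below are assumptions.

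**What treatment group means.** It is not defined for this table. Protocol Section 4.1.3 speaks of randomising subjects to treatment groups, and Section 7.6 shows that randomisation is to sequences. SAP Section 7.8.1 uses the term for the treatment columns of the AE tables. Both readings have to be checked.

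**Reading 1: treatment group is BI 1358894 (T) or placebo (R).** Among N completers let *a* take a therapy on T only, *b* on R only and *c* on both.
- Planned rule: T = (a + b + c)/N and R = (a + b + c)/N, so the difference is 0 for any a, b and c. Counting every possible split of 20 completers gave a maximum difference of 0 subjects.
- By period of intake: T = (a + c)/N and R = (b + c)/N, so the difference is (a − b)/N.
- Example with N = 20, a = 6, b = 1, c = 0. Planned rule: 7/20 (35.0%) against 7/20 (35.0%). By intake: 6/20 (30.0%) against 1/20 (5.0%).

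**Reading 1 with single-period subjects.** Keep 15 completers with a = 6, b = 1, c = 0.
- Add 3 subjects dosed only with T (1 taking a therapy) and 2 dosed only with R (none). Planned rule: T (7 + 1)/18 = 8/18 (44.4%), R 7/17 (41.2%). By intake: T (6 + 1)/18 = 7/18 (38.9%), R 1/17 (5.9%).
- Add instead 5 subjects dosed only with T, none taking a therapy. Planned rule: T 7/20 (35.0%), R 7/15 (46.7%). By intake: T 6/20 (30.0%), R 1/15 (6.7%).

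The columns can now differ, but only because of the single-period subjects. In the last case the difference points the opposite way from actual use.

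**Reading 2: treatment group is sequence T-R or R-T.** Each user appears once, in the column of his sequence. That column contains his T period and his R period together. If every user's intake moved from his T period to his R period, the table would not change, so it carries no information on treatment.

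**Consistency.** AEs, laboratory data and vital signs are attributed to treatment. Therapies are the exception, and neither document gives a reason.

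**The case against.** The strongest case on the other side has four parts.

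- **The wording may mean less.** The paragraphs just before the rule use treatment period and time intervals for the split into screening, treatment and follow-up. The sentence might mean only that therapies are not divided that way. This is possible, but the text sets treatment periods aside explicitly, and even on this reading no rule assigns a therapy to T or R.
- **Double counting is not certain.** A reader might infer that every therapy will appear under both treatments. The documents do not support that: it needs the treatment-column reading and a subject dosed in both periods. Under the sequence reading no therapy appears twice.
- **The information is not lost.** A reader might infer that a difference in therapy use could not be seen anywhere. That goes too far. Intake times on study days are recorded, and Protocol Section 7.3 and SAP Section 7 provide for individual listings. AEs are tabulated by treatment, including a separate table of other significant AEs, a class that covers those leading to significant concomitant therapy (SAP Section 7.8.1). Headache detail is summarised separately. This stands, with the limit that these displays do not count every therapy, and the general listings are sorted by sequence, subject and visit, so attribution has to be worked out by hand.
- **The PSS is protected by other means.** A reader might infer that the primary comparison is at risk. It is not affected by this table. Restricted medication is handled through the exclusion rules in Protocol Section 7.3 and deviation category D1 in SAP Table 6.2: 1, reviewed subject by subject.

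Concomitant therapy is also in principle not allowed, so counts may be small.

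**Conclusion.** The point holds for the summary table and no further. Under either meaning of treatment group, the table specified in Protocol Section 7.3.4 cannot validly compare therapy use on BI 1358894 with placebo, and the SAP does not repair it. This is a stated rule rather than a missing detail, and it departs from the treatment-at-onset principle set in the same section.

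The consequence is minor. One descriptive safety table in an exploratory trial is affected; no endpoint, estimate or analysis set depends on it. The zero difference holds for subjects dosed in both periods under the treatment-column reading. The user counts in the examples are illustrative, since the documents give no expected rate. It is worth correcting because the correction is nearly free.

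**What to change.** In SAP Section 7.2, and listed as a change in SAP Section 4:

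- Assign each therapy started after first dosing to the phase in Table 6.1: 1 that contains its start time, and tabulate by BI 1358894 and placebo.
- Show previous therapy (started before first dosing) in one overall column.
- Flag therapy taken or ongoing between dosing and the last PSS rating of that period. By the Flow Chart this window runs to 5:30 h after dosing (challenge at 5:00 h, last rating 30 minutes later). A flag limited to the 30 minutes after CCK-4 injection would miss therapy taken in the 5 hours before it, which could equally influence the PSS.

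The cost is a few lines of SAP text and one re-programmed table. No new data are needed: intake times on study days are already recorded, and Protocol Section 8.3.1 already lists the therapy start date among the data for the case report form.

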7.3.5 Pharmacokinetic and pharmacodynamic analyses

For a description of PK and PD analyses, please see [Section 7.3.1](#) and [Section 7.3.3](#).

7.4 INTERIM ANALYSES

No interim analysis is planned.

7.5 HANDLING OF MISSING DATA

7.5.1 Safety

It is not planned to impute missing values for safety parameters.

7.5.2 Pharmacokinetics

Handling of missing PK data will be performed according to the relevant Corporate Procedure [\[001-MCS-36-472\]](#).

PK parameters that cannot be reasonably calculated based on the available drug concentration-time data will not be imputed.

7.5.3 Pharmacodynamics

For the PD endpoints PSS if the period baseline value is missing in treatment period 1, it will be imputed by the corresponding value measured in treatment period 2. If the period baseline value is missing in treatment period 2, it will be imputed by the corresponding value measured in treatment period 1. If a value is missing after CCK-4 injection, this value will not be imputed. If all four assessments after CCK-4 injection are missing for a subject, this subject is not evaluable for this endpoint in this period.

7.6 RANDOMISATION

Subjects will be randomised to one of the 2 treatment sequences in a 1:1 ratio. The block size will be documented in the CTR.

The sponsor will arrange for the randomisation as well as packaging and labelling of trial medication. The randomisation list will be generated using a validated system that uses a pseudo-random number generator and a supplied seed number so that the resulting allocation is both reproducible and non-predictable. Access to the codes will be controlled and documented.

The randomisation list will contain additional blocks to allow for subject replacement (refer to [Section 3.3.5](#)).

Proprietary confidential information © 2019 Boehringer Ingelheim International GmbH or one or more of its affiliated companies

7.7 DETERMINATION OF SAMPLE SIZE

It is planned to enter a total of 20 subjects in the trial, because this sample size is considered sufficient to achieve the aims of this exploratory trial. At least 15 subjects need to be evaluable for the primary objective of this trial.

Based on this sample size, the probability to observe a meaningful reduction in PSS sum intensity score after a single dose of BI 1358894 when compared to placebo is given in [Table 7.7: 1](#) for N=20 subjects and in [Table 7.7: 2](#) for N=15 subjects.

For these calculations, the following assumptions are made. A total of N subjects are evaluable in this cross-over study. The standard deviation of the maximum change from baseline of the treatment contrast of PSS relative to placebo is 20%. The maximum change from baseline for PSS sum intensity score relative to placebo is 0% after the placebo treatment. Six different scenarios are displayed.

Table 7.7: 1 Probability to observe a difference in the primary endpoint $\leq 20\%$, $20\% - 40\%$ and $> 40\%$ relative to placebo for different scenarios and a sample size of N=20 evaluable subjects.

True maximum change from baseline relative to placebo		Probability to observe a relative mean difference (BI 1358894 vs. Placebo)		
BI 1358894	Placebo	$\leq 20\%$	20% - 40%	$> 40\%$
10%	0%	70.9	23.6	5.5
18%	0%	54.4	33.9	11.7
28%	0%	33.0	41.5	25.5
33%	0%	23.8	41.2	35.0
46%	0%	8.2	28.9	62.9
52%	0%	4.5	21.0	74.5

Table 7.7: 2 Probability to observe a difference in the primary endpoint $\leq 20\%$, $20\% - 40\%$ and $> 40\%$ relative to placebo for different scenarios and a sample size of N=15 evaluable subjects.

True maximum change from baseline relative to placebo		Probability to observe a relative mean difference (BI 1358894 vs. Placebo)		
BI 1358894	Placebo	$\leq 20\%$	20% - 40%	$> 40\%$
10%	0%	68.2	23.3	8.6
18%	0%	53.8	30.9	15.4
28%	0%	35.3	36.1	28.6
33%	0%	27.1	35.9	37.0
46%	0%	11.6	27.3	61.2
52%	0%	7.3	21.3	71.4

Proprietary confidential information © 2019 Boehringer Ingelheim International GmbH or one or more of its affiliated companies

The calculations were performed using R version 3.3.2. The R code for the sample size calculations will be documented in a separate file and stored in the Trial Master File (TMF).

8. INFORMED CONSENT, TRIAL RECORDS, DATA PROTECTION, PUBLICATION POLICY, AND ADMINISTRATIVE STRUCTURE

The trial will be carried out in compliance with the protocol, the ethical principles laid down in the Declaration of Helsinki, in accordance with the ICH Harmonized Guideline for Good Clinical Practice (GCP), relevant BI Standard Operating Procedures (SOPs) and other relevant regulations. Investigators and site staff must adhere to these principles.

Standard medical care (prophylactic, diagnostic, and therapeutic procedures) remains the responsibility of the subject's treating physician.

The investigator will inform the sponsor immediately of any urgent safety measures taken to protect the trial subjects against any immediate hazard, as well as of any serious breaches of the protocol or of ICH GCP.

The Boehringer Ingelheim transparency and publication policy can be found on the following web page: trials.boehringer-ingelheim.com. The rights of the investigator and of the sponsor with regard to publication of the results of this trial are described in the investigator contract. As a general rule, no trial results should be published prior to archiving of the CTR.

The terms and conditions of the insurance coverage are made available to the investigator and the subjects, and are stored in the ISF.

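### The sample-size tables cannot come from the stated 20% standard deviation; they reproduce only with a contrast SD of about 80%

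*Protocol*

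**What the plan says.** Protocol section 7.7 plans 20 subjects "because this sample size is considered sufficient to achieve the aims of this exploratory trial" and requires at least 15 evaluable. It then offers Tables 7.7: 1 and 7.7: 2 as "the probability to observe a meaningful reduction in PSS sum intensity score after a single dose of BI 1358894" compared with placebo, for N=20 and N=15.

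The assumptions given for both tables are:

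- The design is a cross-over, and N counts the people who can be analysed.
- On variability: "The standard deviation of the maximum change from baseline of the treatment contrast of PSS relative to placebo is 20" per cent.
- On the placebo response: "The maximum change from baseline for PSS sum intensity score relative to placebo is 0% after the placebo treatment".
- Six true effects: 10, 18, 28, 33, 46 and 52%.

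No formula is printed; the section says the R code will be filed in the Trial Master File. The SAP neither restates nor corrects the assumption, and its introduction sends the reader to the protocol for sample-size planning.

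**The concern.** The quantity given an SD of 20% is the treatment contrast itself, and each subject in the cross-over supplies one contrast. The mean of N contrasts then has standard error 20/√N, about 4.5 points at N=20. Against that, the printed probabilities are far too spread out. With a true effect of 10%, an observed mean above 40% lies (40−10)/4.47 = 6.7 standard errors away and is essentially impossible, yet Table 7.7: 1 gives it 5.5%.

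These tables are the only quantitative support in the documents for 20 subjects and for the floor of 15. Protocol section 7.2 plans no confirmatory test and rests interpretation on two-sided 90% confidence intervals, so expected precision is the whole design argument. If the SD is 20%, the tables badly understate what the trial can show. If it is 80%, the text overstates precision fourfold, and the trial can barely separate its own three bands.

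**Working it through.** **Inputs (all from protocol section 7.7).** Contrast SD 20%; N = 20 and 15; placebo change 0%; true effects 10, 18, 28, 33, 46, 52%; cut-offs at 20% and 40%.

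**Formula.** With SE = SD/√N, the three probabilities are F((20−δ)/SE), F((40−δ)/SE) − F((20−δ)/SE), and 1 − F((40−δ)/SE), where δ is the true effect and F is the normal or t distribution function.

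**Step 1: try to reproduce the tables with SD 20%.** SE = 20/√20 = 4.47 and 20/√15 = 5.16. Results for N=20, normal F (≤20 / 20–40 / >40):

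| True effect | Printed | Recomputed, SD 20% |
|---|---|---|
| 10% | 70.9 / 23.6 / 5.5 | 98.7 / 1.3 / 0.0 |
| 18% | 54.4 / 33.9 / 11.7 | 67.3 / 32.7 / 0.0 |
| 28% | 33.0 / 41.5 / 25.5 | 3.7 / 96.0 / 0.4 |
| 33% | 23.8 / 41.2 / 35.0 | 0.2 / 93.9 / 5.9 |
| 46% | 8.2 / 28.9 / 62.9 | 0.0 / 9.0 / 91.0 |
| 52% | 4.5 / 21.0 / 74.5 | 0.0 / 0.4 / 99.6 |

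At N=15, true 28% gives 6.1/92.9/1.0 against the printed 35.3/36.1/28.6. None of the 36 cells matches to one decimal, and all 12 rows fail. The largest gap is 92.9 − 36.1 = 56.8 points. A t distribution on N−2 degrees of freedom does no better (largest gap 54.8).

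**Step 2: solve for the SD the tables imply.** Fitting the SE freely to each table, with t on N−2 degrees of freedom:

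- N=20: SE 17.87, so SD = 17.87 × √20 = 79.9.
- N=15: SE 20.71, so SD = 20.71 × √15 = 80.2.

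Two separate tables give the same SD. A normal F gives about 82%.

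**Step 3: reproduce the tables with SD 80%.** SE = 80/√20 = 17.89 and 80/√15 = 20.66. For N=20 and true 28%, (20−28)/17.89 = −0.447 and (40−28)/17.89 = 0.671. With t on 18 degrees of freedom this gives 33.0/41.5/25.5, exactly as printed. For N=15 and true 28% the result is 35.2/36.2/28.6 (printed 35.3/36.1/28.6). Across all 36 cells the largest difference is 0.1 point, and 28 agree to the printed decimal. Degrees of freedom of N−1 or N−3 also fit closely (largest differences 0.18 and 0.09), so the SD does not depend on that choice.

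**Step 4: try other readings of 20%.**

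| Reading | SE | Cells within 2 points (normal) | Largest gap |
|---|---|---|---|
| SD per treatment, contrast SD 28% | 20√(2/N) | 0 of 36 | 45.3 |
| Two parallel groups of N/2 | 2×20/√N | 1 of 36 | 31.0 |
| 20% is a fixed standard error | 20 | 33 of 36 | 3.4 |

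The last is close, but a fixed standard error would make the two tables identical. They differ, and in proportion to 1/√N.

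**Step 5: what it means for precision.** The approximate half-width of the 90% interval is t(0.95, N−2) × SD/√N:

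| N | SD 20% | SD 80% |
|---|---|---|
| 20 | 1.734 × 4.47 = ±7.8 | 1.734 × 17.89 = ±31.0 |
| 15 | 1.771 × 5.16 = ±9.1 | 1.771 × 20.66 = ±36.6 |

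At ±31.0 the interval spans 62 points, about three times the width of the 20–40% band.

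**The case against.** The arithmetic is not open to serious dispute, but its importance can be. The trial is exploratory, section 7.7 sets no power target or go/no-go threshold, and the primary model estimates its own residual variance, so neither figure enters the analysis. If the tables are right, they already show the reader how uncertain the result will be, and only one sentence is wrong. If 20% is right, the tables are merely pessimistic. All of that is true. It limits the damage to the planning rationale, but it does not reconcile the sentence with the tables.

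A second point concerns where the 20% came from. It could be a standard error from 16 subjects mislabelled as an SD, because 20 × √16 = 80. The documents give no source for the figure, so this is only a possibility. It is algebraically the same contrast SD of 80%, and the sentence would still be wrong.

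Third, one cell comes close under SD 20%: N=20, true 18%, middle band, 32.7 against 33.9. On a tolerance of 2 points, then, 35 of 36 cells fail rather than all 36. The other two cells in that row miss by more than 11 points.

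**Conclusion.** The concern holds. The stated contrast SD of 20% and the two printed tables cannot both be right; the tables imply an SD four times as large. With t on N−2 degrees of freedom, only contrast SDs between 76% and 84% keep every cell within 2 points of print (77.5% to 85.5% with a normal F).

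This rests on reading the SD as the protocol words it, as the SD of the within-subject treatment contrast. Under another formula the same standard errors would correspond to about 57% per treatment, or about 40% for two parallel groups; neither is 20%. The t distribution is inferred from the fit, not stated. Conversion damage is not a plausible cause: each row sums to 100 within rounding, and both tables fit one model. The documents do not show which side is in error. Because these tables carry the whole numerical case for 20 subjects and for the minimum of 15, the section is wrong as written and needs correcting.

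**What to change.** Check the R code that section 7.7 says will be archived, and correct whichever side is wrong.

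- **If the tables are right:** change the stated contrast SD to 80% and give its source. If the 20% was a standard error, say so and give the number of subjects it came from.
- **If 20% is right:** replace both tables from the code, using the same distribution as before. The SD 20% rows shown above use a normal approximation, and t on 18 degrees of freedom moves the N=20 rows by up to about 1.3 points. They show the size of the change and are not final entries.

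In either case, print the formula and the distribution used, and put the expected 90% interval half-width for N=20 and N=15 beside the tables. The half-widths are an addition, not part of the correction, but section 7.2 makes intervals the basis of interpretation.

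The cost is protocol wording and, at most, two recomputed tables. The number of subjects, the conduct of the trial and the analysis model stay as they are. The possible price is that a stated figure becomes less favourable.
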